5. TRIAL SCHEDULE

Detailed trial schedule is given in table 1, page 7. All trial visits and measurements are part of the routine investigation and follow up of children with EAA, except the following:

Screening (Inpatient, day -21 to -2)

The following parameters have to be measured, data has to be collected and documented:

- Patient information and informed consent with the use of the consent form for each age group
- Inclusion/exclusion criteria have to be checked
Randomization must occur directly after consent to the study is given, at least 1 week before the first dose of oral prednisolone; this is necessary to allow for preparation and shipping of the study medication.

Baseline (Inpatient, day -4 to -2)

- The patient or his parents should fill out the questionnaire for evaluation of Quality-of-life
- The patient or his parents should fill out the questionnaire for evaluation of health economics

Discharge (Inpatient, day 1)

- Trial medication will be provided to the patient

Personal contact (day 56 (35-74))

Expert allergen consultation and education at home with control, if the elimination of allergen has been successful

Telephone contact (day 126 (119, 133))

- Vital signs (Height, weight, RR, pulse, temperature), measured by the parents
- Documentation of adverse events

Visit 3 (day 84 (74-94)

- The patient or his parents should fill out the questionnaire for evaluation of Quality-of-life
- The patient or his parents should fill out the questionnaire for evaluation of health economics

Visit 4 (day 168 (148-188)

- The patient or his parents should fill out the questionnaire for evaluation of Quality-of-life
- The patient or his parents should fill out the questionnaire for evaluation of health economics
- End of trial (final visit)

Long term follow up (annually)

- The patient or his parents should fill out the questionnaire for evaluation of Health economics
- The patient or his parents should fill out the questionnaire for evaluation of Quality-of-life
- Build a cohort into adulthood

6. TRIAL METHODS

6.1 Assessment of efficacy

The primary analysis variable is the improvement in FVC (difference after 6 months and baseline). The 6 months and baseline FVC values will be given in percent deviation from the norm values tabulated by Quanjer PH., et al. 2013. FVC will be measured by performing a standardized spirometry with defined quality criteria according to the ATS/ERS guideline. Therefore a standard operation procedure will be provided.

For the evaluation of the quality of life a standardized questionnaire, the “PedsQL”, will be used.

6.2 Assessment of safety

6.2.1 Adverse events

6.2.1.1 Definitions

Adverse Event (AE)

According to GCP, an adverse event (AE) is defined as any untoward medical occurrence in a subject treated with a pharmaceutical product and which does not necessarily have a causal relationship with this treatment. An AE can be any unfavourable and unintended sign (including an abnormal laboratory finding), symptom, or disease temporally associated with the use of a medicinal (investigational) product, whether or not related to the medicinal (investigational) product.

An AE may be:

- a new symptom or a new diagnosis
- a new medical condition or an accident
- a change in laboratory parameters
- an intercurrent illness or accident
- worsening of a medical condition/diseases existing before the start of the clinical trial
- recurrence of a disease
- an increase in frequency or intensity of episodic diseases.

Surgical procedures themselves are not AEs; they are therapeutic measures for conditions that require surgery. The condition for which the surgery is required may be an AE. Planned surgical measures permitted by the clinical trial protocol and the condition(s) leading to these measures are not AEs, if the condition leading to the measure was present before inclusion in the trial. In the latter case the condition should be reported as medical history.

Change in laboratory parameters: The criteria for determining whether an abnormal test finding should be reported as an adverse event are as follows:

- Test result is associated with accompanying symptoms, and/or
- Test result requires additional diagnostic testing or medical/surgical intervention, and/or
- Test result leads to a change in trial dosing outside of protocol-stipulated dose adjustments, or discontinuation from the trial, significant additional concomitant drug treatment, or other therapy, and/or
- Test result is considered to be an adverse event by the investigator or sponsor.
- Progression of EAA under treatment should not be reported as an adverse event. However, if EAA leads to a fatal outcome during the trial or within the safety reporting period, then disease progression should be reported as an adverse event and as a serious adverse event with outcome “death”.

Serious adverse event (SAE)

A serious adverse event (SAE) is one that at any dose (including overdose):

- results in death
- is life-threatening¹
- requires subject hospitalization or prolongation of existing hospitalization²
- results in persistent or significant disability/incapacity³ or
- is a congenital anomaly/birth defect
- is an important medical event⁴.

Comment:

Death is an outcome of an event. The event that resulted in death should be recorded and reported as an SAE.

¹“Life-threatening” means that the subject was at immediate risk of death at the time of the serious adverse event; it does not refer to a serious adverse event that hypothetically might have caused death if it were more severe.

²If the admission is pre-planned (i.e., elective or scheduled surgery arranged prior to start of the trial) or not associated with an adverse event (e.g., social hospitalisation for purpose) or results in a hospital stay less than 12 hours, the serious criterion “hospitalisation” is not fulfilled. However, it should be noted that invasive treatment during a hospitalisation may fulfil the criteria of “medically important” and may be reportable as a serious adverse event dependent on clinical judgement.

An inpatient rehabilitation program per se does not fulfil the seriousness criterion "hospitalization". In this case the investigator should evaluate carefully whether the reason for the inpatient rehabilitation program has to be documented as an AE/SAE.

³"Persistent or significant disability or incapacity" means that there is a substantial disruption of a person's ability to carry out normal life functions. The irreversible injury of an organ function (e.g., paresis, diabetes, cardiac arrhythmia) fulfils this criterion.

⁴Medical and scientific judgement should be exercised in deciding whether expedited reporting is appropriate in situations where none of the outcomes listed above occurred. Important medical events that may not be immediately life-threatening or result in death or hospitalization but may jeopardize the subject or may require intervention to prevent one of the other outcomes listed in the definition above should also usually be considered serious. Examples of such events include allergic bronchospasm requiring intensive treatment in an emergency room or at home, convulsions that do not result in subject hospitalization, or the development of drug dependency or drug abuse. A diagnosis of cancer during the course of a treatment should be considered as medically important.

Clarification of the onset and end date of AEs and SAEs

The onset date of the AE is defined as the onset of signs and symptoms or a change from baseline. The onset date of the SAE is defined as the date the signs and symptoms/diagnosis became serious, i.e., met at least one of the ICH criteria for seriousness.

The end date of the AE is defined as the date when the symptoms resolve, or the event is considered stable. The end date of the SAE is defined as the time the seriousness criteria are no longer applicable.

The end date of the SAE must not be later than the end date of the corresponding AE.

AEs and SAEs that are on-going at the time of death are considered not resolved or resolving.

Clarification of the difference in meaning between "serious" and "severe":

The terms "serious" and "severe" are not synonymous but are often used interchangeably. The term 'severe' is often used to describe the intensity (severity) of a specific event; the event itself, however, may be of relatively minor significance (such as severe headache). This is not the same as "serious", which is based on subject/event outcome or action criteria usually associated with events that pose a threat to a subject's life or functioning. Seriousness (not severity) serves as a guide for defining regulatory reporting obligations."

Suspected Unexpected Serious Adverse Reaction (SUSAR)

A SUSAR is every SAE with an at least possible relationship to the investigational medicinal product which is unexpected.

An unexpected serious adverse reaction is any adverse reaction, the nature or severity of which is not consistent with the applicable product information (i.e., the Investigator's Brochure or the current SmPC).

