2.2 Secondary objectives

The secondary objective(s) of the trial is/are

- a) To evaluate the completeness and knowledge of standardized and pediatric allergen elimination in families with a child with EAA.
- b) To evaluate the treatment of EAA with systemic steroids compared to placebo at 3 months.
- c) To evaluate the safety of the treatment of EAA with outpatient usage of systemic steroids compared to placebo

This study is a prospective, multicenter, randomized, double-blind, placebo-controlled parallel-group study.

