4.4 Open rescue treatment if lung function does not improve

With removal of the allergen by hospitalization and cleaning of the home from offending allergens which is usually done during the initial hospital stay, and after application of the 3d steroid boost to all subjects, a steady improvement in lung function is anticipated. This will be closely monitored by monthly lung function measurements in the first 3 months and at 6 months or additional visits at the discretion of the treating physician. FVC (% predicted) is expected to increase from visit to visit.

If this is not the case, continuing allergen exposure must be considered and a re-evaluation of the allergen elimination has to be performed.

If there is no appropriate improvement of lung function despite appropriate allergen elimination, an open rescue treatment with oral prednisolone (0.5 mg/kg bw/d) should be given till the patient's lung function improves. An alternative may be pulsed methylprednisolone (10 mg/kg bw/d). Extra visits at the discretion of the treating physician may be scheduled.

If the result of the oral prednisolone is not satisfying, re-evaluation of the diagnosis and possibly de-blinding of the study medication should be considered. Alternative medication, including steroid sparing drugs may be considered.

All rescue treatments necessary will be recorded and the cumulative amount of steroids necessary used as a secondary outcome variable.

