6.2.1.5 *Immediate reporting of SAEs by investigator*

SAEs must immediately (within 24 hours of the investigator's awareness) be reported to:

**IZKS Mainz
[name]
55131 Mainz
[contact]**

The initial SAE Report should be as complete as possible including the essential details of subject's identification (screening number, random number), the serious adverse event (medical term, diagnosis), the trial medication and the assessment of the causal relationship between the event and the trial medication. The SAE report must be reviewed and signed by the investigator.

The investigator should provide related additional information on the clinical course and the outcome of each SAE as soon as possible (Follow up report).

The "Serious Adverse Event Form" is provided in the Investigator Site File.

Worsening of a sign or symptom of the condition under treatment will normally be measured by efficacy parameters. However, if the outcome fulfils the definition of "serious adverse event", it must be reported as such.

6.2.1.6 *Immediate Reporting of pregnancy by investigator*

Any **pregnancy** diagnosed in a female subject during treatment with the investigational product must be reported immediately using the “Pregnancy Reporting Form” to:

IZKS Mainz
[name]
55131 Mainz
[contact]

Pregnancy occurring during the clinical trial, although not considered a SAE, must be reported within the same timelines as a serious adverse event. The outcome of a pregnancy should be followed up carefully and abnormal outcome of mother or child should be reported if any.

6.2.1.7 *Documentation of Abuse, Misuse, Overdose and Medication Error*

All special events such as study medication abuse, misuse, overdose and medication errors including dilution errors and infusion rate errors have to be documented in the subject's CRF and source documents. If any abuse, misuse, overdose, or medication errors lead to an adverse event, then the event has to be documented and reported as AE/SAE.

6.2.2 *Other safety data*

Routine physical examination and laboratory determination as specified above at study visits.

6.2.2.1 *Safety evaluation and Reporting by sponsor*

The sponsor will ensure that all legal reporting requirements are met. According to GCP the sponsor is responsible for the continuous safety evaluation of the investigational product(s) and the clinical trial.

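### Protocol sections 6.2.1.1 and 6.2.1.5 give opposite reporting rules for serious, non-fatal worsening of EAA

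*Protocol*

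**What the plan says.** **Section 6.2.1.1, Definitions.** "Progression of EAA under treatment should not be reported as an adverse event". The next sentence gives the only exception: "if EAA leads to a fatal outcome during the trial or within the safety reporting period", the progression is reported both as an AE and as an SAE with outcome death. The same section lists worsening of a pre-existing disease among the things an AE may be.

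**Section 6.2.1.1, seriousness criteria and footnote 2.** Besides death, the criteria cover life-threatening events, hospitalisation or its prolongation, disability, congenital anomaly and important medical events. Footnote 2 removes some admissions from the hospitalisation criterion, among them one "not associated with an adverse event (e.g., social hospitalisation for purpose".

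**Section 6.2.1.5, Immediate reporting of SAEs.** "Worsening of a sign or symptom of the condition under treatment will normally be measured by efficacy parameters". It continues: "However, if the outcome fulfils the definition of" a serious adverse event, "it must be reported as such". Nothing here is limited to fatal outcomes.

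**Section 6.2.1.3, Period of observation.** AE collection runs from first intake, given as day 0, to visit 3, described as the final visit after six months. In section 5 visit 3 is day 84, the final visit is visit 4 on day 168, and trial medication is handed out at discharge on day 1.

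**Section 2.2.** One secondary objective reads: "To evaluate the safety of the treatment of EAA with outpatient usage of systemic steroids compared to placebo".

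**The concern.** Naming death as the one exception implies that every non-fatal progression, however serious, stays outside AE reporting. Section 6.2.1.5 implies the reverse for any worsening that meets a seriousness criterion. Investigators reading different sections would report the same clinical event differently.

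In most placebo-controlled trials placebo is the control. Here the synopsis makes it the experimental intervention and prednisolone the control, with a non-inferiority hypothesis. The foreseeable harm of the experimental arm is worsening of the disease itself, and section 6.2.1.1 removes that kind of event from the AE record unless the patient dies. If serious worsening were more frequent on placebo, leaving it out would make placebo look safer in the section 7.4 tables. Even with no difference between arms, the counts would depend on which section each site applied. With about 40 sites planned for 45 patients, roughly one patient per site (45/40 ≈ 1.1), differences in site practice feed almost directly into the totals.

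**Working it through.** The protocol states no figure on this point, so the check is mainly a comparison of text.

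**1. Apply both rules to the same event.**

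| EAA worsening | Section 6.2.1.1 | Section 6.2.1.5 | Agree? |
|---|---|---|---|
| Not serious | Not an AE | Left to efficacy measures | Yes |
| Serious, fatal | AE and SAE | SAE | Yes |
| Serious, non-fatal (life-threatening, hospitalised, disabling, medically important) | Not an AE | SAE | **No** |

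The conflict is confined to the third row.

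**2. Does another passage settle it?** The protocol treats an SAE as a kind of AE:
- Section 6.2.1.4 calls for the SAE form when an adverse event is serious, refers back to 6.2.1.1 for that, and requires the form in addition to the AE page.
- Section 6.2.1.1 requires the SAE end date to be no later than that of the corresponding AE.
- Footnote 2 withholds the hospitalisation criterion where no adverse event lies behind the admission.

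A site that applies the 6.2.1.1 exemption first has no AE page and no corresponding AE, and for an admission it has footnote 2 as a reason to say the criterion is not met. It can conclude that 6.2.1.5 is never triggered. No passage states an order of precedence.

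**3. Size per event.** Inputs: 45 patients to be allocated (section 3.2), 1:1 (section 3.5.1). Assumption: all 45 are dosed and split 22 and 23. One patient whose only SAE goes unreported changes that arm's SAE proportion by:
- 1/23 = 4.35%
- 1/22 = 4.55%

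That is about 4.3 to 4.5 percentage points. The protocol gives no rate of serious non-fatal worsening, and none is assumed here, so this is not an estimate of total under-reporting.

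**4. Visit label in section 6.2.1.3.** Nominal gap between visits 3 and 4: 168 − 84 = 84 days. Across the visit windows it is 148 − 94 = 54 to 188 − 74 = 114 days. Read by visit number alone, AE collection would stop about 12 weeks before the six-month visit. The accompanying words point to six months, and section 5 documents AEs at the day-126 telephone contact, so the number is a wrong label and not an earlier stop. No loss of observation time is claimed.

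**5. Day of first intake.** In Table 1 day 0 closes the steroid-pulse period, and section 4.2.4 says the pulse is not trial medication. Section 5 hands out trial medication on day 1. The two statements do not match.

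**The case against.** **Section 6.2.1.5 overrides.** It is the operative reporting section, it addresses the treated condition directly, and it says must where 6.2.1.1 says should. Many investigators would read it that way. But the protocol does not say so, 6.2.1.1 restricts its own exception to death, and the SAE form depends on there being an AE as 6.2.1.1 defines it. The override is a possible reading, not a stated rule.

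**The exemption may be narrower than it looks.** It is a bullet in the list of criteria for abnormal test findings, and the same section counts worsening of a pre-existing disease as a possible AE. The placement is odd and may be accidental. Yet the sentence concerns disease progression in general, and its exception for death goes well beyond test results. These features add to the uncertainty.

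**Footnote 2 is a weak link.** Its example is a social admission, and it touches only the hospitalisation criterion. Both points are fair. The conflict does not need the footnote, which only gives a site one more reason not to report.

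**The direction of bias is not shown.** Reporting is blinded, a tilt needs more serious worsening on placebo, and the protocol points both ways: section 7.1 thinks it extremely improbable that prednisolone will be worse within the study period, while section 1.2 suggests prednisolone may promote chronic disease. This stands, so the tilt is a conditional risk. The AE analysis is also descriptive, and worsening is recorded elsewhere. Section 4.4 says: "All rescue treatments necessary will be recorded and the cumulative amount of steroids necessary used as a secondary outcome variable".

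**A separate document may clarify.** Section 6.2.2.1 refers SAE workflow to one that is not shown. It may help sites in practice, but the protocol text would still contradict itself.

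**The visit and day slips are clerical.** Agreed. They would not merit a finding alone.

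**Conclusion.** The contradiction is real and should be corrected. Serious, non-fatal worsening of EAA is excluded from AE reporting by section 6.2.1.1 and must be reported under section 6.2.1.5, with no rule of precedence. The sections agree on non-serious progression and on fatal outcomes.

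The effect is limited to AE/SAE reporting and the section 7.4 tables. The primary FVC analysis is untouched, and FVC, rescue steroid use and withdrawal reasons (section 3.6.3) still capture the worsening. The total number of affected patients cannot be derived from the protocol. The 4.3 to 4.5 points per unreported patient rests on all 45 being dosed and split 22/23. Any tilt towards placebo rests on the further, untested assumption that serious worsening is more frequent on placebo.

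Confidence in the textual conflict is high. Its effect on the safety comparison is plausible but not quantified.

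**What to change.** 1. **Section 6.2.1.1:** replace the fatal-only exception with the rule already in 6.2.1.5. EAA worsening that meets any seriousness criterion is reported as an SAE; non-serious progression stays with the efficacy measures. Move the sentence out of the list on laboratory changes.
2. **Footnote 2:** state that an admission for EAA worsening counts as associated with an adverse event, so that it enters the existing section 7.4 tables.
3. **Section 6.2.1.3:** reconcile the visit number with section 5, where the six-month final visit is visit 4, and reconcile day 0 for first intake with the handing-out of trial medication on day 1.

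The cost is a wording amendment, notified to the ethics committee and, where applicable, the competent authority (section 10.5), a notice to sites, and possibly a few more SAE forms. No visit, assessment, treatment or analysis changes.

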6.2.1.2 Assessment of AEs by investigator

Subjects must be carefully monitored for adverse events by the investigator. The intensity of the adverse events and the causal relation to trial medication and/or procedures are to be assessed.

Intensity/Severity

The intensity of an AE will be assessed by the investigator as follows:

Mild: Temporary event which is tolerated well by the subject and does not interfere with normal daily activities.

Moderate: Event which results in discomfort for the subject and impairs his/her normal activity.

Severe: Event which results in substantial impairment of normal activities of subject.

If the event is serious, the severity reported in the adverse event must be consistent with the severity included in the adverse event report.

Causal relation to trial medication/procedures

The assessment of the relationship of an adverse event to the administration of study drug is a clinical decision based on all available information at the time of the documentation. Factors to be considered in assessing the relationship of the adverse event to study drug include:

- The temporal sequence from drug administration: The investigator has to consider, if the event occurred before first intake of study medication or long time after last intake. Additionally the length of time from drug exposure to event should be evaluated in the clinical context of the event.
- Recovery on discontinuation (de-challenge), recurrence on reintroduction (re-challenge): Subject's response after drug discontinuation (de-challenge) or subjects response after drug re-introduction (re-challenge) should be considered in the view of the usual clinical course of the event in question.
- Underlying, concomitant, intercurrent diseases: Each report should be evaluated in the context of the natural history and course of the disease being treated and any other disease the subject may have.
- Concomitant medication or treatment: The other drugs the subject is taking or the treatment the subject receives should be examined to determine whether any of them may be suspected to cause the event in question.

Positive causal relationship:

An assessment of 'related' implies a reasonable possibility of a causal relationship between the event and the investigational medicinal product (IMP).

This means that there are facts (evidence) or arguments to suggest a causal relationship, such as:

- A close temporal relationship
- A common drug reaction to the IMP
- No plausible alternative cause

Negative causal relationship:

An assessment of 'not related' means that there is no reasonable possibility of a causal relationship between the event and the investigational medicinal product.

This includes for example:

- Another cause of the adverse event is more plausible
- A temporal sequence cannot be established with the onset of the adverse event and administration of the study treatment
- A causal relationship is considered biologically implausible.

6.2.1.3 *Period of observation*

In this trial, the period of observation for collection of adverse events extends from first intake of study medication (day 0) up to visit 3 (final visit after 6 months).

If the investigator detects a serious adverse event in a trial subject after the end of the period of observation, and considers the event possibly related to the prior trial, he should contact the sponsor to determine how the adverse event should be documented and reported.

6.2.1.4 *Documentation of AEs and Follow up*

All AEs (whether serious or not) reported by the subject or detected by the investigator will be documented on the appropriate pages of the case report form (CRF). AEs must also be documented in the subject's medical records.

If the adverse event is serious (see Section 6.2.1.1), the investigator must complete, in addition to the "Adverse Event Page", a "Serious Adverse Event Form" at the time the serious adverse event is detected.

Every attempt should be made to describe the adverse event in terms of a diagnosis. If a clear diagnosis has been made, individual signs and symptoms will not be recorded unless they represent atypical or extreme manifestations of the diagnosis, in which case they should be reported as separate events. If a clear diagnosis cannot be established, each sign and symptom must be recorded individually.

All subjects who have adverse events, whether considered associated with the use of the investigational products or not, must be monitored to determine the outcome. The clinical course of the adverse event will be followed up according to accepted standards of medical practice, even after the end of the period of observation, until a satisfactory explanation is found or the investigator considers it medically justifiable to terminate follow-up, but no longer than 90 days after the end of the trial.

Should the adverse event result in death, a full pathologist's report should be supplied, if possible.

6.2.1.5 *Immediate reporting of SAEs by investigator*

SAEs must immediately (within 24 hours of the investigator's awareness) be reported to:

**IZKS Mainz
[name]
55131 Mainz
[contact]**

The initial SAE Report should be as complete as possible including the essential details of subject's identification (screening number, random number), the serious adverse event (medical term, diagnosis), the trial medication and the assessment of the causal relationship between the event and the trial medication. The SAE report must be reviewed and signed by the investigator.

The investigator should provide related additional information on the clinical course and the outcome of each SAE as soon as possible (Follow up report).

The "Serious Adverse Event Form" is provided in the Investigator Site File.

Worsening of a sign or symptom of the condition under treatment will normally be measured by efficacy parameters. However, if the outcome fulfils the definition of "serious adverse event", it must be reported as such.

6.2.1.6 *Immediate Reporting of pregnancy by investigator*

Any **pregnancy** diagnosed in a female subject during treatment with the investigational product must be reported immediately using the “Pregnancy Reporting Form” to:

IZKS Mainz
[name]
55131 Mainz
[contact]

Pregnancy occurring during the clinical trial, although not considered a SAE, must be reported within the same timelines as a serious adverse event. The outcome of a pregnancy should be followed up carefully and abnormal outcome of mother or child should be reported if any.

6.2.1.7 *Documentation of Abuse, Misuse, Overdose and Medication Error*

All special events such as study medication abuse, misuse, overdose and medication errors including dilution errors and infusion rate errors have to be documented in the subject's CRF and source documents. If any abuse, misuse, overdose, or medication errors lead to an adverse event, then the event has to be documented and reported as AE/SAE.

6.2.2 *Other safety data*

Routine physical examination and laboratory determination as specified above at study visits.

6.2.2.1 *Safety evaluation and Reporting by sponsor*

The sponsor will ensure that all legal reporting requirements are met. According to GCP the sponsor is responsible for the continuous safety evaluation of the investigational product(s) and the clinical trial.

The sponsor Safety Management of IZKS Mainz on behalf of the sponsor will conduct the management of SAEs and the expedited reporting as required by German Drug Law (AMG) and GCP regulation (GCP-V). Suspected unexpected serious adverse reactions (SUSARs) and safety issues as defined by GCP-V are determined for expedited reporting: The competent authority and the ethics committees should be notified as soon as possible but not later than 15 calendar days if the event is non-fatal and 7 calendar days if it was fatal.

All investigators will be informed within the same timeframe.

The marketing authorization holder of the IMP should be informed.

Work flow and procedures concerning SAE management will be described in a separate document.

During the clinical trial the Safety Management of IZKS Mainz on behalf of the sponsor will submit the Development Safety Update Report (DSUR) including a list of all serious adverse reactions to the ethics committee(s), the competent authority (BfArM) and DMC once a year.

6.2.2.2 *Emergency procedures*

During and following a subject's participation in the trial, the investigator should ensure that adequate medical care is provided to a subject for any AEs including clinically significant laboratory values. The investigator should inform a subject when medical care is needed for intercurrent illness(es) of which the investigator becomes aware.

Emergency Unblinding:

If it is medically imperative to know what trial medication the subject is receiving, the investigator or authorized person should open the sealed unblinding codes. The investigator or the person who

breaks the blind must record the date and the reasons for doing so in the CRF, in the subject's medical record and on the unblinding codes.

